9.6 Pharmacodynamics

Pharmacodynamic parameters are not evaluated in this study.

9.7 Pharmacogenomics

The final disposition of samples will be conducted per local regulations.

Details on processes for collection and shipment of these samples can be found in Section 9.8.

[REDACTED]

[REDACTED]

[REDACTED]

[REDACTED]

[REDACTED]

[REDACTED]

[REDACTED]

[REDACTED]

[REDACTED]

[REDACTED]

[REDACTED]

[REDACTED]

[REDACTED]

[REDACTED]

[REDACTED]

[REDACTED]

[REDACTED]

[REDACTED]

[REDACTED]

[REDACTED]

[REDACTED]

[REDACTED]

[REDACTED]

[REDACTED]

[REDACTED]

[REDACTED]

9.9 Medical Resource Utilization and Health Economics

Evaluating quality of life (QoL) in oncology clinical studies is becoming increasingly important to understand the impact of benefit/risk from the participant perspective. Participant reported outcomes will be captured through the use of three validated self-reported questionnaires: the Functional Assessment of Cancer Therapy-General (FACT-G), the NCCN Functional Assessment of Cancer Therapy- Kidney Symptom Index (FKSI-19) and the EuroQoL Group’s EQ-5D (3L version).

The FACT-G is a 27-item questionnaire that measures general cancer health related quality of life. It is one of the most widely used HrQoL cancer specific scales and has been validated in numerous types of cancer participants, across cultures, and in many languages. The scale is a compilation of general questions divided into four primary HrQoL dimensions: Physical Well-Being, Social/Family Well-Being, Emotional Well-Being, and Functional Well-Being. Summary scores can be calculated for each domain in addition to a single overall summary score.

The NCCN FKSI-19 is a 19-item scale that measures tumor specific HrQoL in kidney cancer participants. The FKSI-19 uses five Likert-type response categories that range from “not at all” to “very much”. Participants are asked to circle the response category that best characterizes their response over the last 7 days on 19 items that include symptoms such as lack of energy, fatigue, appetite, coughing, shortness of breath, pain, nausea and ability to work. General health status will be measured using the EQ-5D.

The EQ-5D is a standardized instrument for use as a measure of self-reported general health status. The EQ-5D comprises 5 dimensions (mobility, self-care, usual activities, pain/discomfort, and anxiety) and a visualanalog rating scale (VAS). The utility data generated from the EQ-5D is recommended for and commonly used in cost effectiveness analysis.

Healthcare resource utilization data (eg, hospitalizations, non-protocol specified medical visits, etc.) will be collected for all randomized participants. Specifically, healthcare resource utilization is evaluated based on the number of medical care encounters such as hospital admissions and their duration, outpatient visits, diagnostic tests and procedures, concomitant medications and reasons for the encounters.

Medical resource utilization associated with medical encounters, will be collected in the CRF by the investigator and study-site personnel for all participants throughout the study. Protocol-mandated procedures, tests, and encounters are excluded.

The data collected may be used to conduct exploratory economic analyses and will include:

- Number and duration of medical care encounters, including surgeries, and other selected procedures (inpatient and outpatient)
- Duration of hospitalization (total days length of stay, including duration by wards; eg, intensive care unit)
- Number and character of diagnostic and therapeutic tests and procedures
- Outpatient medical encounters and treatments (including physician or emergency room visits, tests and procedures, and medications)].

10 STATISTICAL CONSIDERATIONS

10.1 Sample Size Determination

Approximately 102 participants will be randomized to the 2 treatment arms in a 1:1 ratio in order to target 100 treated participants (50 per arm). This number of treated participants was chosen to achieve a sufficient level of precision for estimating the difference in rates of infusion-related reactions between the two treatment arms. Fifty treated participants per arm will allow estimation of the rate difference within 95% confidence limits of \pm -20% or less and will be supplemented by a qualitative clinical assessment of the type and severity of events to evaluate benefit-risk. The 20% limit represents what is considered to be a clinically meaningful difference in the rates of infusion-related reactions.

In previously submitted Phase 2/3 studies of nivolumab in combination with ipilimumab (CA209069 and CA209067), AEs in the MedDRA Anaphylactic Reaction SMQ (broad scope) with onset within 2 days after sequential dosing of nivolumab 1 mg/kg combined with ipilimumab 3 mg/kg were reported in 24% of treated participants. In the current study, if the observed rate of infusion reactions is equal to 24% among 50 treated participants in each arm, then the 95% CI for the difference in rates of infusion reactions between arms will be (-16.7%, 16.7%).

Table 10.1-1 shows the precision that the sample size of 50 treated participants per arm will provide for estimating infusion reaction rates and rate differences between the treatment arms under different assumed observed rates.

Table 10.1-1: 95% CI for Rates and Rate Differences when Observed in 50 Participants per Arm

Arm A (Co-administration, FRC)	Observed AE Rate (95% CI)		Observed Rate Difference (95% CI)
	Arm A	Arm B (Sequential administration)	
24% (13.1%, 38.2%)	22% (11.5%, 36.0%)	2%	2% (-14.5%, 18.5%)
24% (13.1%, 38.2%)	24% (13.1%, 38.2%)	0%	0% (-16.7%, 16.7%)
26% (14.6%, 40.3%)	24% (13.1%, 38.2%)	2%	2% (-15.0%, 19.0%)
30% (17.9%, 44.6%)	28% (16.2%, 42.5%)	2%	2% (-15.8%, 19.8%)
30% (17.9%, 44.6%)	30% (17.9%, 44.6%)	0%	0% (-18.0%, 18.0%)

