This number of treated participants was chosen to achieve a sufficient level of precision for a descriptive analysis to estimate the difference in rates of AEs in the Broad Scope MedDRA Anaphylactic Reaction SMQ between the two treatment arms. Fifty treated participants per arm will allow estimation of the rate difference within 95% confidence limits of $\pm 20\%$ or less and will be supplemented by a qualitative clinical assessment of the type and severity of events to evaluate benefit-risk. The 20% limit represents what is considered to be a clinically meaningful difference in the rates of infusion-related reactions.

Treatment Arms and Duration:

Study treatment: This trial is a two-arm, open-label, randomized study:

Part 1:

- **Treatment Arm A:** FRC single infusion (mix of nivolumab and ipilimumab in 3:1 ratio in that order) administered intravenously over 60 minutes
- **Treatment Arm B:** nivolumab (3 mg/kg infused over 60 minutes) followed by ipilimumab (1 mg/kg infused over 30 minutes) administered intravenously with a 30-minute interval waiting period between the two separate infusions
- Note: Cycles will be defined as three weeks in the combination period, Part 1

Part 2:

- Following four doses of the combination participants will switch to nivolumab 480 mg flat dose infused over 30 minutes q 4 weeks. There will be a 6-week interval wait time after the completion of the 4 combination doses prior to beginning the nivolumab monotherapy.
- Note: Cycles will be defined as four weeks in the flat dosing period, Part 2

Discontinuation of Participants from Treatment:

Participants who advance to Part 2 will be treated for up to disease progression or unacceptable toxicity, whichever comes first. Once a patient has discontinued from treatment, he or she will continue to be followed for overall survival (OS) for approximately 5 years. All reasonable effort will be made to maintain contact with participants during this follow-up period via phone calls, faxes, or emails.

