## 4 ENDPOINTS

### 4.1 Primary Endpoint: MedDRA Anaphylactic Reaction Broad Scope SMQ AE Incidence Rate

The primary endpoint of the study is the incidence of AEs in the Broad Scope MedDRA Anaphylactic Reaction SMQ occurring within 2 days after dosing during the combination, Part 1 period. This incidence rate is defined as number of subjects who experienced at least 1 AE in the MedDRA Anaphylactic Reaction broad scope SMQ with onset on the day of or within 2 days after any study therapy infusion during the combination period (Part 1) divided by number of treated subjects. For reference, the terms currently included in the MedDRA Anaphylactic Reaction SMQ based on MedDRA version 19.0 are listed in [Table 4.1-1](#).

The analysis of the primary endpoint will occur when all subjects who are still on-treatment complete Part 1 period.

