## 5 SAMPLE SIZE AND POWER

Approximately 102 subjects will be randomized to the 2 treatment arms in a 1:1 ratio in order to target 100 treated subjects (50 per arm). This number of treated subjects was chosen to achieve a sufficient level of precision for a descriptive analysis to estimate the difference in rates of AEs in the Broad Scope MedDRA Anaphylactic Reaction SMQ between the two treatment arms. Fifty treated subjects per arm will allow estimation of the rate difference within 95% confidence limits of +/- 20% or less and will be supplemented by a qualitative clinical assessment of the type and severity of events to evaluate benefit-risk. The 20% limit represents what is considered to be a clinically meaningful difference in the rates of infusion-related reactions.

In previously submitted Phase 2/3 studies of nivolumab in combination with ipilimumab (CA209069 and CA209067), AEs in the MedDRA Anaphylactic Reaction SMQ (broad scope) with onset within 2 days after sequential dosing of nivolumab 1 mg/kg combined with ipilimumab 3 mg/kg were reported in 24% of treated subjects. In the current study, if the observed rate of infusion reactions is equal to 24% among 50 treated subjects in each arm, then the 95% CI for the difference in rates between arms will be (-16.7%, 16.7%).

Table 5-1 shows the precision that the sample size of 50 treated subjects per arm will provide for estimating rates and rate differences between the treatment arms under different assumed observed rates.

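### Reactions recorded only under an infusion-reaction or general hypersensitivity term fall outside the visible 2-day comparison of arms, although the sample-size text speaks of infusion reactions; one supplementary analysis would cover them

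*Protocol*

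**What the plan says.** **Endpoint.** SAP 4.1 counts a participant with "at least 1 AE in the MedDRA Anaphylactic Reaction broad scope SMQ with onset on the day of or within 2 days" after any Part 1 infusion, over all treated. The Protocol defines it the same way in the synopsis, Table 4-1 and 10.3.2. The term list is printed in Protocol Table 10.3.2-1 and SAP Table 4.1-1.

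**Sample-size text.** Protocol 10.1 gives the aim as "precision for estimating the difference in rates of infusion-related reactions between the two treatment arms" and describes Table 10.1-1 as showing precision "for estimating infusion reaction rates and rate differences between the treatment arms under different assumed observed rates". The planning rate of 24% comes from two earlier studies and is introduced as a rate of "AEs in the MedDRA Anaphylactic Reaction SMQ (broad scope) with onset within 2 days after sequential dosing" (same words in Protocol 10.1 and SAP 5). The next sentence renames it: "if the observed rate of infusion reactions is equal to 24% among 50 treated participants in each arm". SAP 5 does the same: "if the observed rate of infusion reactions is equal to 24% among 50 treated subjects in each arm".

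**The limit.** The synopsis states: "The 20% limit represents what is considered to be a clinically meaningful difference in the rates of infusion-related reactions". Protocol 5.2, Protocol 10.1 and SAP 5 repeat this. The synopsis, Protocol 5.2 and SAP 5 first say that the quantity being estimated is the difference in broad-scope SMQ rates; Protocol 10.1 does not.

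**Supplement.** The precision statement is to be "supplemented by a qualitative clinical assessment of the type and severity of events to evaluate benefit-risk". The text does not say whether events outside the SMQ are part of that assessment.

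**The concern.** The trial asks whether one co-infusion differs in safety from two sequential infusions; the SAP's research hypothesis is that there is no clinically relevant difference. Infusion and hypersensitivity reactions are the obvious events of interest, and Protocol Table 2-2 asks sites to watch for them for 48 hours after dosing. The sample-size text says these are the events the study is sized for.

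The endpoint, however, is a fixed list of preferred terms. If a site records a reaction by its diagnosis, such as an infusion reaction, and that diagnosis is not on the list, the participant does not count. A cough or rash within 2 days does count. What is at stake is whether the main between-arm comparison covers the reactions that its own justification names. In an open-label trial (Protocol 7.3) any additional terms should be chosen before the results are examined.

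**Working it through.** **1. The plan's own figures.** With 50 treated per arm and 24% in each, the unstratified 95% half-width is 1.96 × √(2 × 0.24 × 0.76 / 50) = 0.167. This gives (−16.7%, 16.7%), as stated in Protocol 10.1 and SAP 5. The other four table rows reproduce as well. Randomized number: 100 / (1 − 0.015) = 101.5, so 102. The half-width is largest at 50% in both arms: 1.96 × √(2 × 0.5 × 0.5 / 50) = 19.6 points. The claim of 20% or less therefore holds at any rates, whatever the events are called. The planned primary interval uses CMH weighting, so these half-widths are approximations to it.

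**2. Labels.** The infusion-reaction wording is used nine times.

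| Section | Times | Attached to |
|---|---|---|
| Protocol 10.1 | 5 | precision aim, 20% limit, 24% rate, its CI, Table 10.1-1 |
| SAP 5 | 2 | 20% limit, 24% rate |
| Synopsis | 1 | 20% limit |
| Protocol 5.2 | 1 | 20% limit |

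**3. Term list.** A count of SAP Table 4.1-1 gives 86 terms, 11 narrow and 75 broad. None contains the word infusion. One contains hypersensitivity: *Type I hypersensitivity*. Protocol 7.4.5 names ten ways an infusion reaction might show. Four are on the list (rash, pruritus, hypotension, bronchospasm); six are not (fever, chills, rigors, headache, arthralgias, hypertension).

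**4. Where an unlisted reaction would appear.**
- Part 1 AE summaries (SAP 7.6.8): 30-day window.
- Grade 3-5 endpoints (SAP 4.2.2, 4.2.3): only if severe, and with no 2-day window.
- Infusion interruptions and rate reductions (SAP 7.4.2.2): only if the infusion was changed.
- Extra characterization in SAP 7.6.1: limited to events that already meet the primary criteria.

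None of these gives a 2-day rate difference with a confidence interval.

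**5. Possible size (illustration).** Assume that participants with only unlisted-term events make up between 0% and 3.2% of each arm. The upper value is the combination figure for hypersensitivity/infusion reactions in Protocol 7.1.1. It is generous, because it treats all those reactions as lying outside the SMQ, and no time window is stated for it. At 3.2%:
- Expected participants per arm: 50 × 0.032 = 1.6.
- Combined rate: 24% + 3.2% = 27.2%.
- Half-width: 1.96 × √(2 × 0.272 × 0.728 / 50) = 17.4 points, against 16.7.

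**6. Method for the added terms alone.** Take 2/50 against 1/50. Clopper-Pearson gives 0.5% to 13.7% and 0.1% to 10.6%. The unstratified Newcombe interval for the difference of 2.0 points is −7.0 to 11.6. For comparison, simulating the Mantel-Haenszel risk difference with assumed strata of 17/17/16 per arm gives 96.7% coverage at 3.2% in both arms, but about 86% at 4% against 2%. The shortfall comes from having so few events.

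**The case against.** The strongest reply is that the wording is shorthand. Three of the four sample-size sections open with the SMQ, and the 20% limit then refers back to that difference. Even Protocol 10.1 introduces the 24% as an SMQ rate. Nothing is tested (SAP 7.1: no p-values, descriptive intervals), so 20% is not a formal margin. This stands: relabelling on its own is editorial, and a reader who inferred two competing estimands would be going beyond the text.

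Second, coverage may be better than the printed list suggests. The list in Protocol 7.4.5 is open-ended. The SMQ also holds dyspnoea, flushing, urticaria, wheezing and angioedema, and a reaction with fever and rash counts if the rash is recorded. The visible text does not say whether sites enter the diagnosis, the symptoms or both. Protocol 5.5.5 (the rationale for this endpoint), SAP 4.3.3, a row of Protocol 10.3.2 and the Core Safety SAP cannot be seen. SAP 7.6.9 and 7.6.12 (select AEs, other events of special interest) defer to the last of these. This also stands, and it is why the number of missed events is left open and a cross-reference could suffice. It does not alter the printed term list.

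Third, an extra composite and table may hold almost nothing. That is possible, but they need no new data.

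**Conclusion.** The point holds as a cheap improvement. On the printed MedDRA 19.0 list, a reaction recorded only under an infusion-reaction or general hypersensitivity term is left out of every visible 2-day comparison between arms, while the sample-size text presents that comparison as one of infusion reactions. The number of such events is unknown and may be small. Under the generous assumption above it is 1.6 participants per arm, and each is 1/50 = 2 points.

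Four stronger readings are not supported:
- **The sample size or precision is wrong.** All the figures reproduce, and ±20% holds at any rates.
- **Infusion reactions go unanalysed.** They appear in other tables, and the unseen documents may cover them further.
- **Comparing 24% with 3.2% shows how far the two event sets diverge.** The 24% pools two studies with a 2-day window; the 3.2% is from one of them with no window stated.
- **CMH fails for the added terms because strata would be empty.** The estimate remains defined when individual strata have no events. The reason to avoid it for the added terms alone is the very small number of events.

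Confidence is high on the labels and moderate on the coverage gap, because of the text that cannot be seen.

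**What to change.** Keep the primary endpoint and the sample size.

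1. **Supplementary analysis (Protocol 10.3.2, SAP 7.6.1).** Use the same Part 1 2-day window, all-treated denominator and CI methods as the primary. Count any broad-SMQ term or a listed infusion-reaction or general hypersensitivity preferred term. Name the added terms in advance and recheck them against the MedDRA version at database lock, since SAP 7.6.1 uses the latest version.
2. **Added-terms-only events.** Report counts by arm and worst grade with Clopper-Pearson intervals. Give any difference only with a small-count method, such as unstratified Newcombe, which SAP 7.5.1 already names for ORR subgroups.
3. **Labels.** In Protocol 10.1 and SAP 5, call the 24%, its CI and the precision table broad-SMQ AE rates. In all four sections, state that the 20% limit refers to that rate difference.

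If the Core Safety SAP already gives a 2-day by-arm comparison of these terms, a cross-reference replaces items 1 and 2.

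Cost: nine phrases in four sections, a short paragraph in each document, and one or two tables from AE data already collected. The downside is a second figure beside the primary one, and a table that may hold very few events.

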10.2 Populations for Analyses

The first (primary) analysis will be carried out for primary endpoint and safety related secondary endpoints when all participants who are still on-treatment complete Part 1 period. The final analysis will be carried out for efficacy related secondary endpoints when all participants have at least 9 months of follow-up.

Since the primary objective will be addressed by a safety endpoint, the primary endpoint analysis will be based on all treated participants. For consistency, the secondary endpoints will use the same analysis population as the primary endpoint (ie all treated participants).

Population	Description
All Enrolled Participants	All participants who signed an informed consent form and were registered into the IRT.
All Randomized Participants	All participants who were randomized to any treatment group. This is the primary dataset for efficacy listings.
All Treated Participants	All participants who received at least one dose of any study medication. This is the primary dataset for analysis of study conduct, study population, efficacy (including secondary endpoints), exposure, and safety (including primary endpoint).

Population	Description
Pharmacokinetic Participants	All treated participants with available serum time-concentration data.
Immunogenicity Participants	All treated participants with available ADA data.
Biomarker Participants	All treated participants with available biomarker data.

10.3 Statistical Analyses

The statistical analysis plan will be developed and finalized before database lock and will describe the selection of participants to be included in the analyses, and procedures for accounting for missing, unused, and spurious data. Below is a summary of planned statistical analyses of the primary and secondary endpoints.

10.3.1 Efficacy Analyses

Endpoint	Statistical Analysis Methods
Primary	The primary endpoint is related to safety and there are no primary efficacy endpoints.
Secondary	
One of the secondary endpoint is ORR as determined by investigators. The ORR is defined as the number of participants with a BOR of CR or PR divided by the number of treated participants. The BOR is defined as the best response designation, as determined by the investigator, recorded between the date of randomization and the date of objectively documented progression per RECIST 1.1 or the date of subsequent anti-cancer therapy including radiotherapy, tumor-directed surgery, or systemic anticancer therapy, whichever occurs first. For participants without documented progression or first subsequent therapy, all available response designations will contribute to the BOR assessment. Tumor assessments are scheduled to be performed at Week 12 following randomization, every 8 weeks for the first 12 months and then every 12 weeks until disease progression.
 
Another secondary endpoint is PFS. PFS is defined as the time between the date of randomization and the first date of documented progression, as determined by the investigator, or death due to any cause, whichever occurs first. Participants who die without a reported progression will be considered to have progressed on the date of their death. Participants who did not progress or die will be censored on the date of their last evaluable tumor assessment. Participants who did not have any on study tumor assessments and did not die will be censored on their date of randomization. Participants who started anti-cancer therapy without a prior reported progression will be censored on the date of their last evaluable tumor assessment prior to the

Endpoint	Statistical Analysis Methods
	
initiation of first subsequent anti-cancer therapy including radiotherapy, tumor-directed surgery, or systemic anticancer therapy.
 
Efficacy related secondary endpoints will be analyzed at the time of final analysis when all participants have at least 9 months of follow-up. Descriptive analyses of secondary efficacy endpoints will be performed.
 
ORRs and corresponding 95% exact CIs will be calculated using the Clopper Pearson method for each of the treatment arms. BOR will be tabulated for each treatment group. Associated odds ratios and 95% CIs for Arm A relative to Arm B will be calculated using Cochran-Mantel-Haenszel (CMH) methodology, adjusting for the stratification factors IMDC scores at screening. An estimate of the difference in ORRs and corresponding 2-sided 95% CI will be calculated using CMH methodology, adjusting for the same stratification factors as above.
 
PFS curves for each treatment group will be estimated using the Kaplan-Meier (KM) product limit method. Median PFS and corresponding two-sided, 95% confidence intervals will be computed. Descriptive HRs and corresponding two sided 95% CIs for Arm A relative to Arm B will be estimated using a Cox proportional hazards model, with treatment group as a single covariate, stratified by IMDC scores at screening. PFS rates at 6 months with 95% CIs will be estimated using KM methodology.

[REDACTED]
	
[REDACTED]
 
[REDACTED]
 
[REDACTED]

